5.3.1.2 Collection and Handling of Biomarker and Pharmacogenetic Research Samples

Blood and CSF Biomarker Samples

Blood and CSF samples will be collected as outlined in the Study Activities Table ([Appendix C](#)) and may be utilized to evaluate known and/or novel disease-related or drug-related biomarkers. The biomarker rationale will be discussed in the Biomarker Research Variables Section (Section [5.3.6](#)).

All biomarker samples should be collected, processed, labeled and shipped as outlined in the study-specific laboratory manual, which will be provided separately.

AbbVie (or people or companies working with AbbVie) will store the samples in a secure storage space with adequate measures to protect confidentiality. The samples may be retained while research on ABBV-8E12, or drugs of this class, or AD or related conditions continues, but for no longer than 20 years from the end of the study, or per local requirement.

Blood samples (10 mL) will be collected at Screening and (20 mL) prior to the start of the infusion (0 hour, no more than 30 minutes prior to the start of the infusion) at the time points indicated in the Study Activities Table ([Appendix C](#)). Blood samples collected at Week 96 (Study Completion/PD Visit) may be collected at any time during that visit.

CSF samples (~24 mL) will be collected by lumbar puncture at the time points indicated in the Study Activities Table ([Appendix C](#)). CSF samples collected at Week 14 will be approximately 14 days following the fourth dose. In Cohort 2, CSF sample collection is optional.

Apolipoprotein E (APOE) Pharmacogenetic Sample

One (required) 4 mL whole blood sample will be collected from each subject at study Day 1 for APOE pharmacogenetic analysis. This sample will not be used for any testing other than APOE genotypes.

COVID-19 Pandemic-Related Acceptable Protocol Modifications

In the event blood and optional CSF biomarker samples may not be collected due to study modifications related to the COVID-19 pandemic, these samples should be obtained at the next onsite visit.

Optional Pharmacogenetic Research Samples

Subjects will have the option to provide additional samples for pharmacogenetic research. Subjects may still participate in the main study even if they decide not to participate in this optional research.

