5.3.6 Biomarker and Pharmacogenetic Research Variables

5.3.6.1 Biomarker Research Variables

CSF and Plasma Concentration Variables

CSF samples will be assayed for neurofilament light chain (NFL), free tau and total tau, and the ratio of free tau concentration to total tau concentration will also be statistically analyzed. The assessments on free tau and the ratio of free tau to total tau will be done to investigate the binding of ABBV-8E12 to CSF tau. Plasma samples will be assayed for tau and NFL to understand the relationship to disease progression and response to treatment. Plasma samples may also be analyzed for plasma Abeta 40 and Abeta 42 to study relationship with amyloid PET positivity.

CSF and blood samples may be analyzed for biochemical or macromolecular factors (e.g., amyloid beta) related to the pharmacodynamics and safety of ABBV-8E12. Additional CSF, plasma and/or serum evaluations may include analyzing biomarkers related to the pathway(s) targeted by the study drug or believed to be related to the disease or to drug response. Biomarker samples may also be used for non-genetic exploratory research to assess and generate prognostic, predictive, pharmacodynamic, or surrogate biomarker signatures or develop assays. In addition, the information learned from analyzing these samples may be used to investigate factors impacting response to treatment, scientific questions related to various disease where ABBV-8E12 may be investigated, or in the development of new therapies. The results of biomarker testing may not be reported in the clinical study report.

Volumetric MRI

Baseline vMRI measurements and measurements on change from baseline in vMRI measurements for MRIs from Week 28 through Week 96 will be obtained. Measurements will be obtained for whole brain, hippocampus and lateral ventricles. Measurements may be obtained for additional regions.

Tau PET Imaging

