8.1.5 Biomarker Research Analyses

CSF Concentration Variables

An ANCOVA will be performed on CSF concentrations for total tau, free tau, the ratio of free tau concentration to total tau concentration, and NFL for each scheduled time of evaluation during treatment (fourth dose interval and Week 96). For the analysis for the

fourth dose interval, an analysis will be performed for the data of Cohort 1 alone and also for all available data. The observations will be classified by treatment. The baseline value (last value before the first dose of study drug) will be the covariate except for the analysis on the ratio of the free tau and total tau concentrations, in which case the covariate will be the baseline total tau concentration measurement. If the probability distribution for a variable appears to have considerable non-symmetry (skewness coefficient > 0.75 in magnitude), a transformation will be sought so that the transformed variable has an approximately normal distribution. Within the framework of the ANCOVA the means of the four treatments (with adjustment for baseline) will be estimated. For each ABBV-8E12 dose level, the results of the test of the hypothesis of no difference between the dose and placebo will be reported. Also, with the motivation to have a test with good power if the dose response curve is a monotonic function of dose, a test will be performed on a contrast in the four treatment means. With μ_0 , μ_1 , μ_2 and μ_3 denoting the means for placebo, the 300 mg treatment, the 1000 mg treatment and 2000 mg treatment, respectively, the hypothesis that $-3\mu_0 - \mu_1 + \mu_2 + 3\mu_3 = 0$ will be tested at significance level 0.05 against the two-sided alternative hypothesis. The tests on the effects of the 1000 mg dose and the 300 mg dose will not be formally considered unless the statistic on the effect of the 2000 mg dose or the statistic on the contrast in the four means is significant at level 0.050.

Other CSF concentration variables of interest will be analyzed using methodology like that described for the analysis of total tau concentration.

Serum/Plasma Concentration Variables

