Lumbar Puncture/CSF Sample Collection ^f	X							X ⁱ											
APOE Pharmacogenetic Sample			X																
Optional Pharmacogenetic Sample (DNA and RNA) ^j	X		X					X								X			X
Biomarker Plasma and Serum Sample	X		X					X							X				X

Table 2. Study Activities (Continued)

	Screening		Treatment Period ^a (Year 1)																
	Visit 1	Visit 2	Dose 1			Dose 2	Dose 3	Dose 4			Dose 5	Dose 6	Dose 7	Dose 8	Dose 9	Dose 10	Dose 11	Dose 12	Dose 13
Weeks of Study Drug Exposure	N/A	N/A	0	0	2	4	8	12	12	14	16	20	24	28	32	36	40	44	48
	Day -84 to -8	Day -7 to -1 ^c	Day 1 ^c	Days 5 ^d , 15 ^{c,d}		Day 29 ^c	Day 57 ^c	Day 85 ^c	Days 89 ^d , 99 ^d		Day 113 ^c	Day 141 ^c	Day 169 ^c	Day 197 ^c	Day 225 ^c	Day 253 ^c	Day 281 ^c	Day 309 ^c	Day 337 ^c
Blood Samples for ABBV-8E12 Assay ^k			X	C1		X	C1	X	C1		C1		X			X			X
ADA Sample ^k			X	C1 ^l		X	C1	X	C1		C1		X			X			X
Diagnostic Tools and Rating Scales ^m	X	X							X ^q				X			X ^q			X
Columbia Suicide Severity Rating Scale	X		X	C1		X	X	X	C1		X	X	X	X	X	X	X	X	X
Concomitant Medication Review	X	X	X	C1		X	X	X	C1		X	X	X	X	X	X	X	X	X
Adverse Event Monitoring ⁿ	X	X	X	C1		X	X	X	C1		X	X	X	X	X	X	X	X	X

Table 2. Study Activities (Continued)

	Treatment Period ^a (Year 2)												Post-Treatment Follow-Up Period ^{a,b}	
	Dose 14	Dose 15	Dose 16	Dose 17	Dose 18	Dose 19	Dose 20	Dose 21	Dose 22	Dose 23	Dose 24	Completion Visit/PD	Week 104	Week 112
Weeks of Study Drug Exposure	52	56	60	64	68	72	76	80	84	88	92	96	N/A	N/A
	Day 365^c	Day 393^c	Day 421^c	Day 449^c	Day 477^c	Day 505^c	Day 533^c	Day 561^c	Day 589^c	Day 617^c	Day 645^c	Day 673^c	Days 729	Day 785
Physical Exam						X						X		
Neurological Exam			X			X			X			X	X	
Weight & Height ^c	X	X	X	X	X	X	X	X	X	X	X	X		
Vital Signs	X	X	X	X	X	X	X	X	X	X	X	X	X	
12-Lead ECG ^f						X						X	X	
Clinical Laboratory Tests			X			X			X			X	X	
Administer IV Study Drug	X	X	X	X	X	X	X	X	X	X	X			
MRI					X ^h							X		
Tau PET Scan ^o												X ^p		
Lumbar Puncture/CSF ^r												X		
Optional Pharmacogenetic Sample (DNA and RNA) ^j						X						X		
Biomarker Plasma and Serum Sample						X						X		
Blood Samples for ABBV-8E12 Assay ^k						X						X	X	X

Table 2. Study Activities (Continued)

	Treatment Period ^a (Year 2)											Post-Treatment Follow-Up Period ^{a,b}		
	Dose 14	Dose 15	Dose 16	Dose 17	Dose 18	Dose 19	Dose 20	Dose 21	Dose 22	Dose 23	Dose 24	Completion Visit/PD	Week 104	Week 112
Weeks of Study Drug Exposure	52	56	60	64	68	72	76	80	84	88	92	96	N/A	N/A

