6.2 Visit Definitions

Definition of Rx Day (Days Relative to the First Dose of Study Drug)

Rx Day is calculated for each time point as the number of days between the day of the first dose of study drug and the specific time point. For dates before the first dose date of study drug, Rx day = date of time point – first dose date; for dates on or after the first dose date of study drug, Rx day = date of time point – first dose date + 1. Thus, Rx Day is a negative value when the time point of interest is prior to the day of the first study drug dose; Rx Day is a positive value when the time point of interest is on or after the day of the first study drug dose. There is no Rx Day 0. With this defined algorithm, the day of the first dose of study drug will be Rx Day 1.

Rx End Day is calculated for each post-treatment time point as the number of days between the day of the last dose of study drug and the specific time point:

Rx End Day = date of time point – last dose date. With this defined algorithm, the day of the last dose of study drug will be Rx End Day 0.

Definition of Baseline and Final Observation

Unless otherwise specified, for all efficacy analyses and for all safety analyses of the double-blind Treatment Period, "baseline" shall refer to the last non-missing observation prior to the first dose of study drug and "final" for the double-blind Treatment Period shall refer to the last non-missing observation but no more than 45 days after the last dose of the study drug for both efficacy variables and safety variables. The "final" for the post-treatment follow-up period for safety variables shall refer to the last non-missing observation greater than 45 days but no more than 20 weeks after the last dose of study drug.

Randomization and study drug administration are the last activities of Day 1 Visit after the site completes other study procedures and verifies that the subject is eligible to participate in the study. From the definition of "baseline," it is clear that the baseline for a specific measurement is the last non-missing observation taken up to the Day 1 Visit (the

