An ANCOVA model will be used to evaluate CSF concentrations for total tau, free tau and the ratio of free tau concentration to total tau concentration for each scheduled time of evaluation during treatment (fourth dose interval and Week 96). For the analysis for the fourth dose interval, an analysis will be performed for the data of Cohort 1 alone and also for all available data. The observations will be classified by treatment. The baseline value for total tau and free tau (last value before the first dose of study drug) will be the covariate in the case of total tau and free tau, but for the analysis on the ratio the covariate will be the baseline total tau concentration measurement. If the probability distribution for a variable appears to have considerable non-symmetry (skewness coefficient > 0.75 in magnitude), a transformation will be sought so that the transformed variable has an approximately normal distribution. For each ABBV-8E12 dose level, the results of the test of the hypothesis of no difference between the dose and placebo will be reported. Also, with the motivation to have a test with good power if the dose response curve is a monotonic function of dose, a test will be performed on a contrast in the four treatment means. With μ_0 , μ_1 , μ_2 and μ_3 denoting the means for placebo, the 300 mg treatment, the 1000 mg treatment and 2000 mg treatment, respectively, the hypothesis that $-3\mu_0 - \mu_1 + \mu_2 + 3\mu_3 = 0$ will be tested at significance level 0.050 against the two-sided alternative hypothesis. The tests on the effects of the 1000 mg dose and the 300 mg dose will not be formally considered unless the statistic on the effect of the 2000 mg dose or the statistic on the contrast in the four means is significant at level 0.050.

CSF NFL concentration will be analyzed as described above for CSF total tau concentration. The same will be done for other CSF concentration variables for which data are reported, provided that the proportion of measurements that are outside the limits of quantification and the magnitude of the lower limit do not make a conventional analysis of covariance inappropriate.

Analysis of Serum/Plasma Concentration Variables

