An analysis will be performed for plasma total tau concentration and for plasma NFL concentration. If the data are reported for other plasma concentration variables, an analysis like that described for plasma total tau concentration will be performed, provided that the proportion of measurements that are outside the limits of quantification and the magnitude of the lower limit do not make the methodology inappropriate.

A MMRM analysis will be performed on the data from scheduled times of measurement. The model will include the baseline value as a covariate, have classification of subjects by treatment, an effect for time (classification) and will include an effect for the interaction of treatment and time of measurement. The initial model will also allow the regression coefficient for the baseline value to vary with time (an effect for interaction of time and the baseline value), but this feature will be removed from the model if the statistic on this interaction is not significant at level 0.100. The subjects of each treatment group will be viewed as a random sample, and an appropriate structure for the covariance matrix of the measurements of a subject will be selected. Within the framework of this model, the mean across the scheduled times of measurement will be estimated for each treatment. Also, tests on differences of effect among the dose levels (with placebo considered a dose level) will be performed within the framework of the model. Tests on the dose level main effects will be performed as described for dose level effects in the analysis of covariance for CSF free tau concentration and CSF total tau concentration. These same tests will be provided for each time of measurement in the framework of the MMRM model, and the tests for the individual times will be given the greater attention if the statistic on the interaction of treatment and time of measurement is significant at level 0.100.

Analysis of Volumetric MRI Variables

For volumetric MRI variables, descriptive statistics will be provided for the baseline value, for each scheduled time after that and for the changes from baseline. An MMRM analysis will be performed like that described for plasma NFL concentration, but with an additional covariate, estimated total intracranial volume (eTIV), in the model. The

regression coefficient for eTIV will not vary with time, as may be allowed for the vMRI baseline value.

Analysis of Tau PET Scan Variables

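### Plasma tau and NFL are sampled twice before dosing, but the plasma model adjusts for a single, undefined baseline value, so one pre-dose sample appears to go unused

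*SAP*

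**What the plan says.** **Sampling.** The study activities tables (Protocol Appendix C, SAP Table 2) mark the row "Biomarker Plasma and Serum Sample" at Screening Visit 1 (Day -84 to -8) and at Day 1, then at later visits up to Week 96. Protocol 5.3.1.2 confirms it: "Blood samples (10 mL) will be collected at Screening and (20 mL) prior to the start of the infusion".

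**Assays.** Protocol 5.3.6.1: "Plasma samples will be assayed for tau and NFL to understand the relationship to disease progression and response to treatment". It neither includes nor excludes the Screening sample.

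**Model.** For plasma total tau and NFL, SAP 13.0 specifies an MMRM and states: "The model will include the baseline value as a covariate". The baseline slope may vary with time at first, and that interaction is dropped if it is not significant at 0.100. The plasma text does not say which pre-dose value is the baseline.

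**Baseline rules given elsewhere.** SAP 6.2 says baseline "shall refer to the last non-missing observation prior to the first dose of study drug", but its scope is "for all efficacy analyses and for all safety analyses of the double-blind Treatment Period". In SAP 13.0 the explicit rule sits under the CSF heading: "The baseline value for total tau and free tau (last value before the first dose of study drug) will be the covariate". Protocol 8.1.5 likewise states its rule under CSF: "The baseline value (last value before the first dose of study drug) will be the covariate". SAP 6.2 averages values only when they fall on the same day.

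**RBANS and MMSE.** SAP Table 3 schedules both at Screening and again between Day -7 and Day 1. They are efficacy variables, so the SAP 6.2 rule does govern them, and their MMRMs (SAP 10.3.1) use one baseline score.

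**The concern.** A single plasma value is a noisy measure of a subject's starting level. When a second pre-dose value exists and carries information beyond the first, a model that ignores it leaves explainable variation in the residual. Every dose-versus-placebo and trend comparison is then somewhat less precise than it could be.

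Plasma tau and NFL are the fluid biomarkers planned for all subjects. Lumbar puncture is optional in Cohort 2, and SAP 14.0 now expects far fewer tau PET data than were first anticipated. Precision in plasma is therefore worth having. The missing plasma definition also leaves the programmer to choose between two candidate values.

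**Working it through.** **Inputs.** From the documents: two scheduled pre-dose plasma samples, one baseline covariate, and averaging for same-day values only. Assumed, because the documents give no figure: r0 (correlation between Screening and Day 1), rD and rS (correlation of Day 1 and of Screening with a follow-up value). One follow-up visit is treated as an ANCOVA, which approximates the MMRM contrast at that visit.

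**The plan's own figure.** The only power statement (SAP 4.3) concerns CDR-SB. With 100 x (1 - 0.25) = 75 per group, effect sizes 0.45, 0.45 and 0.28, one-sided 0.025/3 per dose and correlation 0.5 from the shared placebo arm, the chance that at least one dose is significant is 80.6%, against about 80% stated. Plasma data do not enter this calculation. No power is stated for plasma tau or NFL.

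**Step 1: equal correlation with follow-up (rS = rD = r1).** Residual variance is proportional to
- Day 1 alone: 1 - r1^2
- both values (here the same as their mean): 1 - 2 r1^2/(1 + r0)

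| r0 | r1 | Day 1 alone | Both | Reduction |
|---|---|---|---|---|
| 0.5 | 0.5 | 0.750 | 0.667 | 11.1% |
| 0.7 | 0.7 | 0.510 | 0.424 | 17.0% |
| 0.8 | 0.8 | 0.360 | 0.289 | 19.8% |
| 0.9 | 0.9 | 0.190 | 0.147 | 22.4% |
| 0.8 | 0.7 | 0.510 | 0.456 | 10.7% |
| 0.8 | 0.5 | 0.750 | 0.722 | 3.7% |
| 0.9 | 0.7 | 0.510 | 0.484 | 5.1% |
| 0.9 | 0.5 | 0.750 | 0.737 | 1.8% |

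A comparison with 80% power would rise to 84.2% at the 10.7% reduction and to 88.9% at the 22.4% reduction.

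**Step 2: Screening less correlated with follow-up.** Take r0 = 0.8 and rD = 0.7, so Day 1 alone leaves 1 - 0.49 = 0.510.
- Both as covariates: 1 - (rD^2 + rS^2 - 2 r0 rD rS)/(1 - r0^2)
- Simple mean, equal variances: 1 - (rS + rD)^2/(2(1 + r0))

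| rS | Both as covariates | Change | Simple mean | Change |
|---|---|---|---|---|
| 0.65 | 1 - 0.1845/0.36 = 0.488 | -4.4% | 1 - 1.8225/3.6 = 0.494 | -3.2% |
| 0.60 | 1 - 0.178/0.36 = 0.506 | -0.9% | 1 - 1.69/3.6 = 0.531 | +4.0% |
| 0.56 | 1 - 0.1764/0.36 = 0.510 | 0.0% | 1 - 1.5876/3.6 = 0.559 | +9.6% |

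The last row is rS = r0 x rD, where Screening adds nothing beyond Day 1. The mean breaks even at rS = sqrt(3.6 x 0.49) - 0.7 = 0.63 and loses precision below that. Two covariates do not lose, apart from degrees of freedom.

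**Step 3: simulation.** With 75 per group and both values as covariates, the variance of the treatment estimate relative to Day 1 alone was 0.903 (r0 0.8, r1 0.7), 0.912 (0.9, 0.8) and 0.772 (0.9, 0.9). The formula gives 0.893, 0.906 and 0.776. All estimates centred on the true difference of zero.

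**Step 4: how much one value already captures.** Relative to both values with equal correlations, Day 1 alone explains r1^2 / [2 r1^2/(1 + r0)] = (1 + r0)/2. That is 80% at r0 = 0.6, 90% at 0.8 and 95% at 0.9.

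**The case against.** The case against acting is serious. A last-value baseline is conventional and valid under randomisation. Plasma tau and NFL are exploratory and outside family-wise error control. The 11% to 22% range needs correlation with follow-up to be as high as between the two pre-dose samples, although follow-up runs to Week 96 and Screening may be 84 days before dosing. All of this stands, and it makes the point one of efficiency only.

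Two stronger readings are tempting and fail. A reader might infer that half of the baseline information is thrown away, because one of two samples is unused. Step 4 shows the unused share of explainable variance to be 5% to 20% for r0 between 0.6 and 0.9. It would reach half only if the samples were uncorrelated. A reader might also infer that SAP 6.2 fixes the plasma baseline. It names efficacy and safety analyses, and the biomarker rule is written for CSF, so for plasma the last-value reading is an analogy.

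Nor do the documents state that Screening plasma is assayed for tau and NFL. The volumes differ (10 mL against 20 mL), and Protocol 5.3.6.1 names another possible use, Abeta 40 and 42 against amyloid PET status. The assay is implied only. The warning against averaging is also right, as Step 2 shows. So is the warning against a shifted baseline for the CDR-SB relationship analyses, where SAP 13.0 wants paired measurements close in time. Neither counts against entering Screening as a second covariate.

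**Conclusion.** The point holds as a low-cost gain in precision and a gap in definition. It is not a bias or validity error. It leaves the primary CDR-SB analysis and its power unchanged.

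Under assumed correlations, entering both pre-dose values lowers contrast variance by about 11% to 22% in the favourable case (r0 = r1 from 0.5 to 0.9), commonly by 1% to 10% when follow-up correlations are lower, and by almost nothing when Screening is redundant given Day 1. Where in this range the trial falls cannot be told from the documents. The gain also depends on Screening plasma being assayed. CSF is unaffected, because only one pre-dose lumbar puncture is scheduled.

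For RBANS and MMSE the second score is certainly collected and the last-value rule certainly applies. The gain there has not been quantified. It may be smaller, because Screening MMSE (22 to 30) and RBANS-DMI (85 or lower) are entry criteria and so restricted in range.

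**What to change.** In SAP 13.0:
- Define the plasma baseline as the last pre-dose value.
- State whether the Screening sample is assayed for tau and NFL. Where it is, add the Screening value as a second covariate in the plasma MMRM, on the scale used for analysis.
- Give a rule that uses the single available value when the other is missing, so that no subject drops out of the model.
- Do not make the simple mean the default.
- Keep the Day 1 value for the change-from-baseline analyses against CDR-SB.

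In SAP 10.3.1, the Screening RBANS and MMSE scores can be added to their own MMRMs in the same way.

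The cost is a few lines of SAP text and about one degree of freedom per added covariate, or one per visit if its slope varies with visit. Assay cost arises only if Screening plasma is not already being assayed. No visit, sample or procedure changes.

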5.6.2 Appropriateness of Measurements

Standard pharmacokinetic, statistical and clinical procedures will be utilized in this study. On-treatment safety evaluations (neurological examinations, adverse event monitoring, ECGs) are scheduled at more frequent intervals for the first 48 subjects enrolled (Cohort 1) to promptly detect potential emerging safety signals.

Overall, choice of instruments to measure key domains of function, cognition, behavior and caregiver distress has been guided by published data on their use in MCI and AD patients. These instruments have shown to be sensitive to the change in Early AD and MCI patients over a period of time.

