- Week 20 Rx Days 127 through 154
- Week 24 Rx Days 155 through 182
- Week 28 Rx Days 183 through 210
- Week 32 Rx Days 211 through 238
- Week 36 Rx Days 239 through 266
- Week 40 Rx Days 267 through 294
- Week 44 Rx Days 295 through 322
- Week 48 Rx Days 323 through 350
- Week 52 Rx Days 351 through 378
- Week 56 Rx Days 379 through 406
- Week 60 Rx Days 407 through 434
- Week 64 Rx Days 435 through 462
- Week 68 Rx Days 463 through 490
- Week 72 Rx Days 491 through 518
- Week 76 Rx Days 519 through 546

- Week 80 Rx Days 547 through 574
- Week 84 Rx Days 575 through 602
- Week 88 Rx Days 603 through 630
- Week 92 Rx Days 631 through 658
- Week 96 Rx Days > 658

For measurements that are planned to be collected during the double-blind treatment period at Weeks 2, 4, 8, 12, 14, 16, 20, 24, 28, 32, 36, 40, 44, 48, 52, 56, 60, 64, 68, 72, 76, 80, 84, 88, 92, and 96, i.e., vital signs and C-SSRS, observations will be mapped to an analysis "week" according to the following windows defined by Rx day.

- Week 2 Rx Days 2 through 21 (Cohort 1 subjects)
- Week 4 Rx Days 22 through 42 (Cohort 1 subjects)
Rx Days 2 through 42 (Cohort 2 subjects)
- Week 8 Rx Days 43 through 70
- Week 12 Rx Days 71 through 91 (Cohort 1 subjects)
Rx Days 71 through 98 (Cohort 2 subjects)
- Week 14 Rx Days 92 through 105 (Cohort 1 subjects)
- Week 16 Rx Days 106 through 126 (Cohort 1 subjects)
Rx Days 99 through 126 (Cohort 2 subjects)
- Week 20 Rx Days 127 through 154
- Week 24 Rx Days 155 through 182
- Week 28 Rx Days 183 through 210
- Week 32 Rx Days 211 through 238
- Week 36 Rx Days 239 through 266
- Week 40 Rx Days 267 through 294
- Week 44 Rx Days 295 through 322
- Week 48 Rx Days 323 through 350
- Week 52 Rx Days 351 through 378
- Week 56 Rx Days 379 through 406

- Week 60 Rx Days 407 through 434
- Week 64 Rx Days 435 through 462
- Week 68 Rx Days 463 through 490
- Week 72 Rx Days 491 through 518
- Week 76 Rx Days 519 through 546
- Week 80 Rx Days 547 through 574
- Week 84 Rx Days 575 through 602
- Week 88 Rx Days 603 through 630
- Week 92 Rx Days 631 through 658
- Week 96 Rx Days > 658

For measurements that are planned to be collected during the double-blind treatment period at Weeks 4, 8, 12, 16, 20, 24, 36, 48, 60, 72, 84 and 96, i.e., clinical laboratory tests, observations will be mapped to an analysis "week" according to the following windows defined by Rx day.

- Week 4 Rx Day 2 through 42
- Week 8 Rx Day 43 through 70
- Week 12 Rx Days 71 through 98

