- Week 16 Rx Day 99 through 126
- Week 20 Rx Days 127 through 154
- Week 24 Rx Days 155 through 210
- Week 36 Rx Days 211 through 294
- Week 48 Rx Days 295 through 378
- Week 60 Rx Days 379 through 462
- Week 72 Rx Days 463 through 546
- Week 84 Rx Days 547 through 630
- Week 96 Rx Days > 630

For measurements that are planned to be collected during the double-blind treatment period at Weeks 2, 4, 8, 12, 24, 36, 48, 72 and 96, i.e., ECG, observation will be mapped to an analysis "week" according to the following windows defined by Rx day.

- Week 2 Rx Days 2 through 21 (Cohort 1 subjects)
- Week 4 Rx Days 22 through 42 (Cohort 1 subjects)
Rx Days 2 through 42 (Cohort 2 subjects)
- Week 8 Rx Days 43 through 70
- Week 12 Rx Days 71 through 126
- Week 24 Rx Days 127 through 210
- Week 36 Rx Days 211 through 294
- Week 48 Rx Days 295 through 420
- Week 72 Rx Days 421 through 588
- Week 96 Rx Days > 588

For vital sign measurements, C-SSRS, ECG, clinical laboratory tests, and MRI that are planned to be collected during the post-treatment follow-up period at Weeks 104, observations will be mapped to an analysis "week" according to the following windows defined by Rx End day.

- Post-Treatment Week 8 Rx End Days > 45

For measurements that are planned to be collected during double-blind treatment period on Weeks 6, 14, 30, 46, 70 and 96, i.e., MRI observation will be mapped to an analysis "week" according to the following windows defined by Rx day.

- Week 6 Rx Days 2 through 70
- Week 14 Rx Days 71 through 154
- Week 30 Rx Days 155 through 266
- Week 46 Rx Days 267 through 406
- Week 70 Rx Days 407 through 581

- Week 96 Rx Days > 581

If more than 1 observation is included in a visit time window, the observation that is closest to the nominal day of the visit will be used in the analysis. If two observations have the same distance to the nominal day of the visit, the last non-missing observation will be used in analyses. If more than 1 observation occurs on the same day, the average will be calculated and used in analyses.

7.0 Demographics, Baseline Characteristics, Subject History, and Previous/Concomitant Medications

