11.6 Analysis for Other Safety Variables

11.6.1 Columbia-Suicide Severity Rating Scale (C-SSRS)

Number and percentage of subjects in the following categories will be summarized for each treatment group and ABBV-8E12 Overall by visit and for the entire study:

- Answered 'Yes' to each C-SSRS item
- Had suicidal ideation (defined as answering 'Yes' to one or more suicidal ideation items)
- Had suicidal ideation only (defined as answering 'Yes' to one or more suicidal ideation items and answering 'No' to all suicidal behavior items)
- Had suicidal behavior (defined as answering 'Yes' to one or more suicidal behavior items)
- Had suicidal ideation or behavior (defined as answering 'Yes' to one or more suicidal ideation or behavior items)

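### SAP 6.2 gives Cohort 1's Day 5 and Day 89 visits no analysis window, so most of their vital signs and C-SSRS drop out of the by-visit tables under a selection rule that does not suit yes/no items

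*SAP*

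**What the plan says.** SAP Tables 1 and 2 schedule Cohort 1 vital signs and C-SSRS on Days 5, 15, 85, 89 and 99, among other days. ECGs are scheduled on Days 5 and 15 but not on Days 89 or 99.

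For vital signs and C-SSRS, SAP 6.2 sets "Week 2 Rx Days 2 through 21 (Cohort 1 subjects" and "Week 12 Rx Days 71 through 91 (Cohort 1 subjects" as the first two relevant windows. Week 14 is "Rx Days 92 through 105 (Cohort 1 subjects". Neither Day 5 nor Day 89 has its own window. The ECG Week 2 window for Cohort 1 is also Days 2–21.

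On choosing among records, SAP 6.2 says "If more than 1 observation is included in a visit time window, the observation that is closest to the nominal day of the visit" is used. Equal distances go to the later record, and several records on one day are averaged.

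The outputs differ by measure:
- SAP 11.6.1: C-SSRS categories "will be summarized for each treatment group and ABBV-8E12 Overall by visit and for the entire study".
- SAP 11.4.1 and 11.5.1: vital signs and ECG are analysed at each double-blind visit and also as minimum, maximum and final value.
- SAP 11.4.2 and 11.5.2: the PCS summaries count a subject with at least one qualifying double-blind observation, and a listing is added.

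**The concern.** The four-day post-infusion visits were added for Cohort 1 only. If the window rule sets them aside whenever the partner visit is present, the by-visit tables cannot show a short-lived change soon after the first or fourth infusion, although the data were collected.

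C-SSRS raises a further problem. Taking the value nearest a nominal day, or averaging two values, is reasonable for a blood pressure. For a yes/no item it means that a yes can be replaced by a no that happens to lie nearer the nominal day, and that a same-day yes and no average to something that is not a category. This affects any window holding more than one record, in either cohort.

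**Working it through.** **Inputs.** Nominal days (SAP Table 2): 15, 29, 57, 85, 99, 113, 141. Tolerances (SAP Tables 1 and 2): ±2 days for Days 5, 15, 89 and 99; ±4 days for other visits, including Day 85. Windows, selection rule and tie rule: SAP 6.2. Cohort 1 size: 48 (SAP 4.2).

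**Step 1: reproduce the plan's windows.** Take midpoints between adjacent nominal days, with the midpoint opening the later window:

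- (15+29)/2 = 22, so Week 2 is Days 2–21
- (29+57)/2 = 43, so Week 4 is Days 22–42
- (57+85)/2 = 71, so Week 8 is Days 43–70
- (85+99)/2 = 92, so Week 12 is Days 71–91
- (99+113)/2 = 106, so Week 14 is Days 92–105
- (113+141)/2 = 127, so Week 16 is Days 106–126

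Every Cohort 1 limit matches. With Day 89 as the Week 12 nominal day, the window would run from (57+89)/2 = 73 to (89+99)/2 − 1 = 93, which does not match. Week 12 is therefore built on Day 85. This has to be inferred, because Table 2 places both Day 85 and Day 89 under 12 weeks of exposure.

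**Step 2: visits held on their nominal days.** Day 5 is |5 − 15| = 10 days from nominal and Day 15 is 0. Day 89 is |89 − 85| = 4 days from nominal and Day 85 is 0. Both early visits lose.

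**Step 3: visits within tolerance, both present.**

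- *Day 5 (Days 3–7) against Day 15 (Days 13–17).* Distances are 8–12 against 0–2. Day 5 is chosen in 0 of 5 × 5 = 25 pairs.
- *Day 89 (Days 87–91) against Day 85 (Days 81–89).* Of 9 × 5 = 45 pairs, 6 have the follow-up on or before the dosing day, leaving 39. Day 89 is chosen in 6: three strictly closer, namely (81,87), (81,88) and (82,87), and three ties that go to the later record, namely (81,89), (82,88) and (83,87). It loses in 39 − 6 = 33.

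**Step 4: alternative timing.** The tables can also be read as timing the follow-up from the actual Dose 4 date. Assuming 4 ± 2 days after it, there are 45 pairs. The follow-up is chosen for Week 12 in 14, loses to the dosing-day record in 21, and in the other 10 falls on Days 92–95, inside Week 14, where it competes with Day 99. All these figures count permitted day pairs; they are not probabilities.

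**Step 5: size.** 48 × 2 = 96 C-SSRS records and 96 vital-sign records at most, plus up to 48 Day 5 ECGs. At 1:1:1:1 this is about 48/4 = 12 subjects per arm.

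**Step 6: effect on a C-SSRS item.** A yes on Day 5 and a no on Day 15 give distances of 10 and 0, so Week 2 shows no.

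**The case against.** The case for leaving the plan alone is that one record per window is a legitimate choice and the effect is small. Several parts of that case stand.

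- **A reader might infer that post-infusion results never reach the by-visit tables.** They do. Days 15 and 99 are post-infusion visits and fill Weeks 2 and 14. Day 89 is chosen in 6 of 39 pairs, and Day 5 or Day 89 is used whenever its partner is missing.
- **A reader might infer that a Day 5 or Day 89 yes also vanishes from the entire-study C-SSRS summary.** The documents do not support this. SAP 6.2 introduces windows for longitudinal analysis, and SAP 11.6.1 states the entire-study summary separately from the by-visit one. It has no visit window to which the rule could apply. What is missing is a start point: SAP 11.6.1 does not limit the summary to assessments after the first dose. Exclusion criterion 9 bars a yes to ideation questions 4 or 5 and recent attempts, so only lesser pre-dose ideation could be counted.
- **A reader might take Protocol 5.6.2 as proof that the design intent is defeated.** It says that certain evaluations are "scheduled at more frequent intervals for the first 48 subjects enrolled (Cohort 1) to promptly detect potential emerging safety signals", but the evaluations it names are neurological examinations, adverse event monitoring and ECGs. It supports the Day 5 ECG point and does not name C-SSRS or vital signs. Prompt detection also rests on the DMC reviews of all available safety data (Protocol 8.1.10), which do not depend on these windows.
- **Symptom-prompted C-SSRS assessments** are not described in either document, so no weight is placed on them.

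These points limit the reach of the finding. They do not explain why scheduled visits should have no place in the by-visit tables, or why a yes/no item should follow a rule suited to continuous data.

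**Conclusion.** The overlap follows directly from the stated windows and rule. When Day 15 is present, Day 5 is always left out of the by-visit tables. Day 89 is left out on nominal timing and in 33 of 39 permitted day pairs, if both visits are scheduled by study day. If the follow-up is timed from the actual dose, it is still not the Week 12 record in 21 + 10 = 31 of 45.

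The loss is confined to by-visit summaries in Cohort 1: at most 96 records for each of vital signs and C-SSRS, and 48 ECGs. Minimum, maximum and PCS outputs for vital signs and ECG still include these records, and so, on its natural reading, does the entire-study C-SSRS summary. Efficacy and adverse event tables are untouched.

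The C-SSRS selection and averaging rule is the more general fault, since it is unsuitable for yes/no items in both cohorts. The point is modest in size but worth correcting.

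**What to change.** 1. Assign Cohort 1's Day 5 and Day 89 vital signs and C-SSRS, and the Day 5 ECG, to their own analysis visits by visit label.
2. Do not use fixed day windows for this. The midpoint method would give a Day 89 window of 87–93, from (85+89)/2 = 87 and (89+99)/2 = 94. Dose 4 visits may fall on Days 81–89, so those on Days 87–89 (3 of 9 permitted days) would be captured as Day 89. For example, with dosing on Day 88 and follow-up on Day 92, the dosing record (distance 1) would beat the follow-up (distance 3), leaving Week 12 empty.
3. For C-SSRS in both cohorts, use the worst response within each window instead of closest-to-nominal selection or same-day averaging.
4. State in SAP 11.6.1 that the entire-study summary uses all assessments after the first dose, and show pre-dose ideation separately.
5. State that the Week 12 nominal day is Day 85.

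The cost is minor SAP wording and programming, and two more columns in the Cohort 1 by-visit tables. A subject who misses Day 15 would have no Week 2 value, where the present rule lets Day 5 stand in for it. No new data are needed and no efficacy result changes.
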